3.2. SECONDARY OBJECTIVES

The secondary objectives are to evaluate the effects of the three sequencing combination treatments on:

- Total Progression-Free Survival (PFS);
- 3 years PFS rate;
- Percentage of patients alive at 3 years;
- Best overall response rate (BORR);
- Duration of response (DoR);
- Toxicity of the investigational medicinal products (IMPs);
- Quality of life and general health status defined by:
 - Health-related quality of life (HRQoL), by means of the 30-item European Organisation for Research and Treatment of Cancer quality of life questionnaire (EORTC QLQ-C30);
 - General health status, by means of the European Quality of Life 5-Dimensions (EQ-5D) questionnaire;
 - Impairment of work productivity and activity, by means of the Work Productivity and Activity Impairment: General Health (WPAI:GH) questionnaire.

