Subjects will be assessed for response by computed tomography (CT) or Magnetic Resonance Imaging (MRI). All measurable and non-measurable lesions must be documented at screening (within 28 days prior to randomization) and re-assessed at each subsequent tumor evaluation (every 8 weeks (+/- 1 week) for the first year, every 12 weeks (+/- 1 week) while the patient is on study). Tumor assessments with CT or MRI scans of the brain, chest, abdomen, and pelvis will be performed until disease progression after the second combo treatment per RECIST v1.1.

For patients who discontinue study treatment for reason other than investigator-determined disease progression, tumor assessments should continue to be performed as scheduled.

Patients will continue to be on study and can be switched to the subsequent therapy after PD as per protocol in both arm A and B.

In case of an interruption of the treatment in arm C, reason other than investigator-determined disease progression, during the first 8 weeks (2 cycles of therapy), patient can continue the study treatment with combo immuno, as scheduled.

For patients with palpable/superficial lesions, clinical disease assessments by physical examination should be performed at baseline and throughout study treatment as clinically indicated. Color photographs with ruler/calipers will be taken at baseline and at all subsequent tumor assessment time points.

The National Cancer Institute Common Toxicity Criteria for Adverse Events (NCI CTC-AE) Version 4.03 will be used to evaluate the clinical safety of the treatment in this study. Patients will be assessed for AEs at each clinical visit and as necessary throughout the study.

Biomarker study

A correlative biological study will be performed for the evaluation of biomarkers on the biological sample available (paraffin-embedded tissue, frozen tissue, blood, serum, etc.). Approximately 80-90 patients will take part in the biomarker study.

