21.1. ADVERSE EVENTS

All adverse events (AEs) reported on eCRF and experienced by the patient on or after the informed consent date will be considered in the analysis. Thus, there will not be derivation to Treatment-emerged Adverse Events (TEAE) and not TEAE.

Adverse event Investigator terms will be assigned to a Preferred Term (PT) and will be classified by primary System Organ Class (SOC) according to the Medical Dictionary for Regulatory Activities (MedDRA) thesaurus, version 20.0 or higher

Counts and percentages will be presented by primary System Organ Class (SOC) and Preferred Term (PT) as defined in MedDRA thesaurus, by treatment arm.

A patient having more than one AE with the same PT will be counted only once in the incidence calculation for that PT. Similarly, if a patient has more than one AE in the same SOC, the patient will be counted only once in the total number of patients with an AE for that SOC.

An AE will be defined “Related” if causality is “Certain”, “Probable” or “Possible”.

The following frequency distributions of adverse events will be provided by treatment arm:

- An overview of AEs including the number of patients with:
 - at least one AE,
 - at least one non-serious AE,
 - at least one AE related to Ipilimumab,
 - at least one AE related to Nivolumab,
 - at least one AE related to Combo Immuno Therapy,
 - at least one AE related to LGX818,
 - at least one AE related to MEK162,
 - at least one AE related to Combo Target Therapy,
 - at least one serious AE (SAE),
 - at least one SAE related to Ipilimumab,
 - at least one SAE related to Nivolumab,
 - at least one SAE related to Combo Immuno Therapy,
 - at least one SAE related to LGX818,
 - at least one SAE related to MEK162,
 - at least one SAE related to Combo Target Therapy,
 - at least one AE leading to hospitalization,
 - at least one AE leading to withdrawal from the study,

- at least on AESI,
and the number of AEs, non-serious AEs, SAEs, AEs related to Ipilimumab, AEs related to Nivolumab, AEs related to Combo Immuno Therapy, AEs related to LGX818, AEs related to MEK162, AEs related to Combo Target Therapy, SAEs related to Ipilimumab, SAEs related to Nivolumab, SAEs related to Combo Immuno Therapy, SAEs related to LGX818, SAEs related to MEK162, SAEs related to Combo Target Therapy, AEs leading to hospitalization, AEs leading to death, AEs leading to study withdrawal, AESIs;
- AEs presented by Primary SOC and PT;

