- AEs related to Ipilimumab presented by Primary SOC and PT;
- AEs related to Nivolumab presented by Primary SOC and PT;
- AEs related to Combo Immuno Therapy presented by Primary SOC and PT;
- AEs related to LGX818 presented by Primary SOC and PT;
- AEs related to MEK162 presented by Primary SOC and PT;
- AEs related to Combo Target Therapy presented by Primary SOC and PT;
- Serious AEs presented by Primary SOC and PT;
- AEs leading to hospitalization presented by Primary SOC and PT;
- AEs leading to death presented by Primary SOC and PT;
- AEs leading to study withdrawal presented by Primary SOC and PT.
- AESIs presented by Primary SOC and PT

The following individual data listings will be produced:

- A listing of all AEs;
- A listing of AEs related to Ipilimumab;
- A listing of AEs related to Nivolumab;
- A listing of AEs related to Combo Immuno Therapy;
- A listing of AEs related to LGX818;
- A listing of AEs related to MEK162;
- A listing of AEs related to Combo Target Therapy;
- A listing of all SAEs;
- A listing of all AEs leading to death;
- A listing of AEs leading to hospitalization;
- A listing of AEs leading to study withdrawal;
- A listing of AESIs.

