Number of SAEs related to Combo LGX818	n	xx	xx	xx
Number of SAEs related to Combo MEK162	n	xx	xx	xx
Number of SAEs related to Combo Target Therapy	n	xx	xx	xx
Number of AEs leading to hospitalization	n	xx	xx	xx
Number of AEs leading to death	n	xx	xx	xx
Number of AEs leading to withdrawal from the study	n	xx	xx	xx
Number of AEs of special interest (AESI)	n	xx	xx	xx
Number of Patients with at Least One AE	n (%)	xx (xx.x%)	xx (xx.x%)	xx (xx.x%)
Number of Patients with at Least One non-serious AE	n (%)	xx (xx.x%)	xx (xx.x%)	xx (xx.x%)
Number of Patients with at Least One AE related to Ipilimumab	n (%)	xx (xx.x%)	xx (xx.x%)	xx (xx.x%)
Number of Patients with at Least One AE related to Nivolumab	n (%)	xx (xx.x%)	xx (xx.x%)	xx (xx.x%)
Number of Patients with at Least One AE related to Combo Immuno Therapy	n (%)	xx (xx.x%)	xx (xx.x%)	xx (xx.x%)
Number of Patients with at Least One AE related to LGX818	n (%)	xx (xx.x%)	xx (xx.x%)	xx (xx.x%)
Number of Patients with at Least One AE related to MEK162	n (%)	xx (xx.x%)	xx (xx.x%)	xx (xx.x%)
Number of Patients with at Least One AE related to Combo Target Therapy	n (%)	xx (xx.x%)	xx (xx.x%)	xx (xx.x%)
Number of Patients with at Least One serious AE (SAE)	n (%)	xx (xx.x%)	xx (xx.x%)	xx (xx.x%)
Number of Patients with at Least One SAE related to Ipilimumab	n (%)	xx (xx.x%)	xx (xx.x%)	xx (xx.x%)
Number of Patients with at Least One SAE related to Nivolumab	n (%)	xx (xx.x%)	xx (xx.x%)	xx (xx.x%)
Number of Patients with at Least One SAE related to Combo Immuno Therapy	n (%)	xx (xx.x%)	xx (xx.x%)	xx (xx.x%)
Number of Patients with at Least One SAE related to Combo LGX818	n (%)	xx (xx.x%)	xx (xx.x%)	xx (xx.x%)
Number of Patients with at Least One SAE related to Combo MEK162	n (%)	xx (xx.x%)	xx (xx.x%)	xx (xx.x%)
Number of Patients with at Least One SAE related to Combo Target Therapy	n (%)	xx (xx.x%)	xx (xx.x%)	xx (xx.x%)
Number of Patients with at Least One AE leading to hospitalization	n (%)	xx (xx.x%)	xx (xx.x%)	xx (xx.x%)
Number of Patients with at Least One AE leading to withdrawal from the study	n (%)	xx (xx.x%)	xx (xx.x%)	xx (xx.x%)
Number of Patients with at Least One AESI	n (%)	xx (xx.x%)	xx (xx.x%)	xx (xx.x%)

Note: a) Percentages are calculated relative to the total number of patients in the SAF population by treatment arm.

b) An AE is defined as "related" to a study drug if relationship is "Certain", "Probable" or "Possible" to that specific drug. Missing data were considered as Related.

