XXX	XXX	XXXXXXXXXX	XXX	XXX	XXX	DDMMYYYY	XXX	XXX	XXX	XXX
XXX	XXX	XXXXXXXXXX	XXX	XXX	XXX	DDMMYYYY	XXX	XXX	XXX	XXX
XXX	XXX	XXXXXXXXXX	XXX	XXX	XXX	DDMMYYYY	XXX	XXX	XXX	XXX
XXX	XXX	XXXXXXXXXX	XXX	XXX	XXX	DDMMYYYY	XXX	XXX	XXX	XXX

Source: XXXX.SAS, Run on DDMMYYYY

Listing 42) Administration with Investigational Products

POPULATION: ITT

Treatment Arm	Site	Patient Number	Visit	IMP	IMP administered ?	If not, reason	Date of dispensation (DDMMYYYY)	Start therapy date (DDMMYYYY)	End therapy date (DDMMYYYY)	Dose	Unit	Administration	Reason for reduction/delay/definite interruption	Reduced dose
XXX	XXX	XXXXXXXX X	XXX	XXX	XXX	XXX	DDMMYYYY	DDMMYYYY	DDMMYYYY	XXX	XXX	XXX	XXX	XXX
				XXX	XXX	XXX	DDMMYYYY	DDMMYYYY	DDMMYYYY	XXX	XXX	XXX	XXX	XXX
				XXX	XXX	XXX	DDMMYYYY	DDMMYYYY	DDMMYYYY	XXX	XXX	XXX	XXX	XXX
				XXX	XXX	XXX	DDMMYYYY	DDMMYYYY	DDMMYYYY	XXX	XXX	XXX	XXX	XXX
				XXX	XXX	XXX	DDMMYYYY	DDMMYYYY	DDMMYYYY	XXX	XXX	XXX	XXX	XXX
XXX	XXX	XXXXXXXX X	XXX	XXX	XXX	DDMMYYYY	DDMMYYYY	DDMMYYYY	XXX	XXX	XXX	XXX	XXX	
XXX	XXX	XXXXXXXX X	XXX	XXX	XXX	DDMMYYYY	DDMMYYYY	DDMMYYYY	XXX	XXX	XXX	XXX	XXX	

Source: XXXX.SAS, Run on DDMMYYYY

Listing 43) LGX818

POPULATION: ITT

Trt Arm	Site	Pt Nr.	Visit	Date of dispensation (DDMMYYYY)	Batch #1 (50 mg)	Batch #2 (100 mg)	Batch #3 (100 mg)	Batch #4 (100 mg)	Batch #5 (100 mg)	Dose	Taken correctly?	If not, reason	Nr. of capsules returned
XXX	XXX	XXXXXXXX	XXX	DDMMYYYY	XXX	XXX	XXX	XXX	XXX	XXX	XXX	XXX	XXX
				DDMMYYYY	XXX	XXX	XXX	XXX	XXX	XXX	XXX	XXX	XXX
			XXX	DDMMYYYY	XXX	XXX	XXX	XXX	XXX	XXX	XXX	XXX	XXX
				DDMMYYYY	XXX	XXX	XXX	XXX	XXX	XXX	XXX	XXX	XXX
			XXX	DDMMYYYY	XXX	XXX	XXX	XXX	XXX	XXX	XXX	XXX	XXX
				DDMMYYYY	XXX	XXX	XXX	XXX	XXX	XXX	XXX	XXX	XXX
XXX	XXX	XXXXXXXX	XXX	DDMMYYYY	XXX	XXX	XXX	XXX	XXX	XXX	XXX	XXX	XXX
XXX	XXX	XXXXXXXX	XXX	DDMMYYYY	XXX	XXX	XXX	XXX	XXX	XXX	XXX	XXX	XXX

Source: XXXX.SAS, Run on DDMMYYYY

Listing 44) MEK162

POPULATION: ITT

Trt Arm	Site	Pt Nr.	Visit	Date of dispensation (DDMMYYYY)	Batch #1 (15 mg)	Batch #2 (15 mg)	Batch #3 (15 mg)	Total Daily Dose	Taken correctly?	If not, reason	Nr. of capsules returned	Diary completed correctly and returned?
XXX	XXX	XXXXXXXX	XXX	DDMMYYYY	XXX	XXX	XXX	XXX	XXX	XXX	XXX	XXX
				DDMMYYYY	XXX	XXX	XXX	XXX	XXX	XXX	XXX	XXX
			XXX	DDMMYYYY	XXX	XXX	XXX	XXX	XXX	XXX	XXX	XXX
				DDMMYYYY	XXX	XXX	XXX	XXX	XXX	XXX	XXX	XXX
			XXX	DDMMYYYY	XXX	XXX	XXX	XXX	XXX	XXX	XXX	XXX
				DDMMYYYY	XXX	XXX	XXX	XXX	XXX	XXX	XXX	XXX
XXX	XXX	XXXXXXXX	XXX	DDMMYYYY	XXX	XXX	XXX	XXX	XXX	XXX	XXX	XXX

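### The only discontinuation category for adverse events is withdrawal from the study, so a toxic stop of a first combination ordinarily reaches no summary table

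*Supplement*

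**What the plan says.** The overview in SAP section 21.1 counts patients with "at least one AE leading to withdrawal from the study". The breakdown by system organ class and preferred term is "AEs leading to study withdrawal presented by Primary SOC and PT", and the overview shell (Table 45) has the row "Number of Patients with at Least One AE leading to withdrawal from the study". Table 55 and Listing 64 use the same category. (Table numbers here are those on the shells; the contents list in section 26 gives 43 and 53 for the same two tables.) No table has a category for stopping a drug, a combination or a treatment period.

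Section 4.4 describes what happens after a stop:

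- In general: "For patients who discontinue study treatment for reason other than investigator-determined disease progression, tumor assessments should continue to be performed as scheduled".
- For a non-progression interruption in Arm C during the first 8 weeks: "patient can continue the study treatment with combo immuno, as scheduled".
- For the other two arms: "Patients will continue to be on study and can be switched to the subsequent therapy after PD as per protocol in both arm A and" (the sentence closes by naming Arm B).

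Sections 3.2 and 3.3 list toxicity of the study drugs as a secondary and a safety objective. At patient level, the adverse event listings carry an 'Action taken' column, and Listing 42 carries, for each drug, "Reason for reduction/delay/definite interruption".

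**The concern.** In a single-regimen trial, withdrawal due to an adverse event and stopping the drug due to an adverse event often nearly coincide. Here every arm is a sequence, and losing one combination to toxicity need not end participation. A summary that recognises only study withdrawal then leaves out a basic tolerability result: how many patients had to give up each combination because of toxicity. The order of the combinations is what is randomised, so a count that could also depend on order would be awkward to read across the columns of Table 45.

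**Working it through.** The plan states no figure on this point, so the check is mainly of the text.

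**Step 1: is a toxic stop captured in another table?** Section 21.1 also tabulates events related to each drug and combination, serious events, hospitalisation, death and events of special interest. None shows whether treatment was stopped. Exposure (section 19) gives durations without reasons, and its overall duration ignores temporary interruptions and dose changes. Compliance covers only the oral drugs. The stop and its reason appear only in listings.

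**Step 2: is a toxic stop of a first combination a study withdrawal?** Under section 4.4, ordinarily not. Scans continue, Arm A and B patients can switch at later progression, and an Arm C patient interrupted in the first 8 weeks can move to Combo Immuno.

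**Step 3: is a toxic stop of the last combination a study withdrawal?** The SAP does not settle this.

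- Against: the rule that scans continue after a non-progression stop is not limited to the first combination.
- For: section 11 and Listing 4 put last dose, trial completion and one primary withdrawal reason together in the end-of-treatment data. AE is one reason offered. Another is consent withdrawn for the study but not for follow-up, so a patient recorded as withdrawn may still be followed.

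**Step 4: what follows under each reading?** The documents give no toxic-stop rates, so this is an illustration on assumptions. Inputs:

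- n = 69 per arm (section 4.2).
- Assumed toxic-stop rate of Combo Immuno, i = 10% to 40%.
- Assumed toxic-stop rate of Combo Target, t = 10%.
- Assumed share reaching the second combination, q = 40% to 70%.
- Rates do not depend on position.

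Toxic stops: Arm A = n(t + q·i); Arm B = n(i + q·t).

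*Reading 1, no toxic stop counts as study withdrawal:* Table 55 shows none of them in either arm.

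*Reading 2, only stops of the last combination count:* counted in Arm A = n·q·i; counted in Arm B = n·q·t.

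| i, t, q | Stops A | Counted A | Stops B | Counted B |
|---|---|---|---|---|
| 10%, 10%, 40% | 69(0.10+0.04) = 9.66 | 2.76 | 9.66 | 2.76 |
| 30%, 10%, 50% | 69(0.10+0.15) = 17.25 | 10.35 | 69(0.30+0.05) = 24.15 | 3.45 |
| 40%, 10%, 70% | 69(0.10+0.28) = 26.22 | 19.32 | 69(0.40+0.07) = 32.43 | 4.83 |

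The share missed is t/(t + q·i) in Arm A and i/(i + q·t) in Arm B. Over the assumed grid it runs from 0.10/0.38 = 26% to 0.10/0.14 = 71% in Arm A, and from 0.10/0.17 = 59% to 0.40/0.44 = 91% in Arm B. With equal 10% rates the two arms show the same count, and 59% to 71% of stops are missing from each. With unequal rates the missed share differs between arms.

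**The case against.** The dependence on position is inferred. It needs a stop of the last combination to be recorded as study withdrawal and a stop of the first not to be, and section 4.4 draws no such line. The SAP rests on protocol version 10.0, which is not among the documents; that protocol or the case report form may define withdrawal. This stands, and it is why the position effect is only one of two possible consequences.

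A reader might go further and infer that Combo Immuno given first will look better tolerated than Combo Immuno given second, by an amount that can be put in percentage points. The documents do not support this. How sites record a last-combination stop is unknown and no stop rates are given. Tables 45 and 55 are by arm with the whole safety set of the arm as denominator, so they contain no contrast of one combination in first and second position.

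It is also fair to say that toxicity is not otherwise ignored: related and serious events are tabulated by drug and combination. Section 8.3 makes all results descriptive, so there is no main tolerability comparison to replace. None of this supplies the missing count, and columns set side by side by arm will be read together whether or not a test is run.

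**Conclusion.** The point holds as a gap in the summary tables. Following the SAP as written, adverse events that permanently end a first combination are ordinarily counted in no summary table. For stops of the last combination the outcome depends on an undefined term: either toxic stops are missed in all arms, or the count can vary with the combination's place in the sequence. Both readings call for the same correction.

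The size cannot be derived from the documents. The figures in the working rest on assumed rates and show only that the omission could be large; they predict neither a direction nor an amount. The data appear to be collected, so the fault lies in the tabulation. It concerns descriptive safety reporting and leaves the overall survival analysis untouched.

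**What to change.** In section 21.1 and Table 45:

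1. Define withdrawal from the study separately from discontinuation of treatment, and say how a stop of the last combination is classified and from which field.
2. Add, by combination within arm, the number and percentage of patients with at least one adverse event leading to permanent discontinuation of that combination. The denominator is the patients who started it. Arm C gives Combo Target in two periods, so these should be shown separately.
3. Derive the rows from 'Action taken' in the adverse event listings and the reason field of Listing 42.

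Rows for adverse events leading to dose reduction or delay are an optional addition from the same fields. The cost is some SAP wording and a few table rows, with no new data collection.

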21.2. LABORATORY EVALUATIONS

Laboratory data will be analyzed on the SAF set.

Descriptive summaries of hematology, blood chemistry, coagulation, thyroid function, Cardiac Muscle Enzyme and endocrine panel will be provided for actual values and changes from baseline at each visit by treatment arm.

Default frequency tabulations will be also provided for urinalysis by treatment group for each visit.

Line listings of laboratory data during the study will be provided.

Presentations for continuous variables will use SI Units: conversion will be provided using the International Laboratory Normal Ranges (SI Unit Conversion Guide, M. Laposata, NEJM, 1992).

To convert from the conventional unit to the SI unit, laboratory specific derivations will be used, multiply by the conversion factor.

Table 3- Hematology: conversion factors

Component	Conventional Unit	Conversion Factor	SI Unit
Hemoglobin	g/dL	10	g/L
Hematocrit	%	0.01	Proportion of 1.0
RBC Count	X 10 ⁶ /μl	1	X 10 ¹² /L
WBC Count	X 10 ³ /μl	1	X 10 ⁹ /L
Neutrophils	X 10 ³ /μl	1	X 10 ⁹ /L
Lymphocytes	X 10 ³ /μl	1	X 10 ⁹ /L
Monocytes	X 10 ³ /μl	1	X 10 ⁹ /L
Eosinophils	X 10 ³ /μl	1	X 10 ⁹ /L
Basophils	X 10 ³ /μl	1	X 10 ⁹ /L
Platelets	X 10 ³ /μl	1	X 10 ⁹ /L

Table 4- Biochemistry: conversion factors

Component	Conventional Unit	Conversion Factor	SI Unit
Glucose	mg/dL	0.05551	mmol/L
Sodium	mEq/L	1	mmol/L
Potassium	mEq/L	1	mmol/L
Calcium	mg/dL	0.2558	mmol/L
	mEq/L	0.5	
Chloride	mg/dL	0.250	mmol/L
	mEq/L	1	
Bicarbonate	mEq/L	1	mmol/L
Magnesium	mg/dL	0.4114	mmol/L
Urea	mg/dL	0.167	mmol/L

BUN	mg/dL	0.357	mmol/L
Uric Acid	mg/dL	59.48	μmol/L
Albumin	g/dL	10	g/L
Creatinine	mg/dL	88.4	μmol/L
Creatinine Clearance	mL/min	0.01667	mL/s
Total Proteins	g/dL	0.01	g/L
Total Bilirubin	mg/dL	17.104	μmol/L
Indirect Bilirubin	mg/dL	17.104	μmol/L
Alkaline phosphatase	units/L	1	U/L
Alanine aminotransferase (ALT)	units/L	1	U/L
Aspartate aminotransferase (AST)	units/L	1	U/L
Gamma-GT	units/L	1	U/L
HDL Cholesterol	mg/dL	0.02586	mmol/L
LDL Cholesterol	mg/dL	0.02586	mmol/L
LDH	Units/L	1	U/L
	Units/L	0.01667	μkat/L
Amylase	Units/L	1	U/L
	Units/L	0.01667	μkat/L
Lipase	Units/L	1	U/L
	Units/L	0.01667	μkat/L

Table 5- Coagulation: conversion factors

Component	Conventional Unit	Conversion Factor	SI Unit
INR	Ratio	1	ratio

aPTT	Seconds	1	seconds
PTT	Seconds	1	seconds
Protrombin time	Seconds	1	seconds
Fibrinogen	g/dL	29.41	μmol/L
	mg/dL	0.01	g/L

Table 6 – Thyroid function test: conversion factors

Component	Conventional Unit	Conversion Factor	SI Unit
TSH	μU/mL	1	mU/L
Free T4	μg/dL	12.87	nmol/L
Free T3	ng/dL	0.01536	nmol/L

Table 7 – Cardiac Muscle Enzyme: conversion factors

Component	Conventional Unit	Conversion Factor	SI Unit
Creatine Kinase	μkat/L	59.988	U/L
	ng/dL	100	ng/mL
Troponin	ng/L	1000	
	μg/L	1	
Creatinin Kinase Isoenzyme	%	0.01	Fraction of 1.00
Myoglobin	ng/mL	17.513	nmol/L

Table 8 – Endocrine panel: conversion factors

Component	Conventional Unit	Conversion Factor	SI Unit
ACTH	pg/mL	0.2202	pmol/L
Total cortisol	μg/dL	27.59	nmol/L

The following parameters will be collected for urinalysis:

- Glucose (Neg, Trace, 1+, 2+, 3+, 4+)
- Protein (Neg, Trace, 1+, 2+, 3+, 4+)
- Blood (Neg, Trace, 1+, 2+, 3+, 4+)
- Bilirubin (Neg, Trace, 1+, 2+, 3+, 4+)
- Ketones (Neg, Trace, 1+, 2+, 3+, 4+)
- Leukocytes (Neg, Trace, 1+, 2+, 3+, 4+)
- UWBC/HPF (Not present, Present) and continuous value if present
- URBC/HPF (Not present, Present) and continuous value if present
- Casts/LPF (Not present, Present) and continuous value if present
- Bacteria (Not present, Present) and continuous value if present
- Other (Not present, Present) and continuous value if present

The following summaries will be provided for urinalysis data by treatment arm:

- Actual and change from baseline by visit for continuous values of UWBC/HPF, URBC/HPF, Casts/LPF, Bacteria and Other, if present;
- Frequency tables by visit for glucose, protein, blood, bilirubin, ketones, leukocytes, UWBC/HPF, URBC/HPF, Casts/LPF, Bacteria and Other.

21.3. CARDIOLOGICAL ASSESSMENTS

ECG and ECHO/MUGA parameters will be analysed on the SAF set.

Descriptive summaries of PR interval (ms), QT interval (ms), QRS interval (ms), QTcB interval (ms), cardiac axis (°), Ejection Fraction Value (%) will be provided for actual values and changes from baseline at each visit by treatment arm.

Default frequency tabulations will be also provided for ECG result (Normal, Abnormal) and interpretation of abnormal ECG (not clinically significant, clinically significant), type of LVEF scan (ECHO, MUGA) and ECHO/MUGA scan interpretation (Normal, Clinically insignificant abnormality, Clinically significant abnormality) by treatment arm.

Line listings of ECG and ECHO/MUGA parameters during the study will be provided.

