21.4. VITAL SIGNS

Vital signs parameters will be analyzed on the SAF set.

Descriptive summaries of the following parameters will be provided for actual values and changes from baseline at each visit by treatment arm:

- Body weight (Kg)
- BMI (kg/m²)
- Systolic Blood Pressure (mmHg)
- Diastolic Blood Pressure (mmHg)
- Heart Rate (bpm)
- Body Temperature (°C)

- Respiratory rate (breaths/min)

A line listing of vital signs during the study will be provided.

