	Min/Max	xx/xx	xx/xx
Follow-up	n	xx	xx
	Mean (SD)	xx.x (x.x)	xx.x (x.x)
	Median	xx.x	xx.x
	Min/Max	xx/xx	xx/xx

Notes:

(*) Change from baseline is calculated relative to Baseline 1 for values between Baseline 1 and Baseline 2; Baseline 2 for values between Baseline 2 and Baseline 3; Baseline 3 for values after Baseline 3. Change from baseline values include only those patients with both a Baseline value and a value for summarized time period.

n represents number of patients contributing to summary statistics.

Source: XXXX.SAS, Run on DDMMYYYY

TABLE 85. ECG Parameters - ARM A

POPULATION: SAF < Note for SAS Programmer: the following must be presented for QT, QRS, QTcB, cardiac axis, Ejection Fraction value as well >

	Statistic	Value	Change from Baseline (*)
PR interval (ms)			
Baseline 1	n	xx	
	Mean (SD)	xx.x (x.x)	
	Median	xx.x	
	Min/Max	xx/xx	
Week 4 - Combo Target	n	xx	xx
	Mean (SD)	xx.x (x.x)	xx.x (x.x)
	Median	xx.x	xx.x
	Min/Max	xx/xx	xx/xx
Week <Every 12 wks> - Combo Target	n	xx	xx
	Mean (SD)	xx.x (x.x)	xx.x (x.x)
	Median	xx.x	xx.x
	Min/Max	xx/xx	xx/xx
Baseline 2	n	xx	
	Mean (SD)	xx.x (x.x)	
	Median	xx.x	
	Min/Max	xx/xx	
Week 4 - Nivolumab + Ipilimumab	n	xx	xx
	Mean (SD)	xx.x (x.x)	xx.x (x.x)
	Median	xx.x	xx.x
	Min/Max	xx/xx	xx/xx
Week <Every 12 wks> - Nivolumab	n	xx	xx
	Mean (SD)	xx.x (x.x)	xx.x (x.x)
	Median	xx.x	xx.x
	Min/Max	xx/xx	xx/xx

Notes:

(*) Change from baseline is calculated relative to Baseline 1 for values between Baseline 1 and Baseline 2; Baseline 2 for values after Baseline 2. Change from baseline values include only those patients with both a Baseline value and a value for summarized time period. n represents number of patients contributing to summary statistics.

Source: XXXX.SAS, Run on DDMMYYYY

TABLE 86. ECG Parameters - ARM B

POPULATION: SAF < Note for SAS Programmer: the following must be presented for QT, QRS, QTcB, cardiac axis, Ejection Fraction value as well >

	Statistic	Value	Change from Baseline (*)
PR interval (ms)			
Baseline 1	n	xx	
	Mean (SD)	xx.x (x.x)	
	Median	xx.x	
	Min/Max	xx/xx	
Week 4 - Nivolumab + Ipilimumab	n	xx	xx
	Mean (SD)	xx.x (x.x)	xx.x (x.x)
	Median	xx.x	xx.x
	Min/Max	xx/xx	xx/xx
Week <Every 12 wks> - Nivolumab	n	xx	xx
	Mean (SD)	xx.x (x.x)	xx.x (x.x)
	Median	xx.x	xx.x
	Min/Max	xx/xx	xx/xx
Baseline 2	n	xx	
	Mean (SD)	xx.x (x.x)	
	Median	xx.x	
	Min/Max	xx/xx	
Week 4 - Combo Target	n	xx	xx
	Mean (SD)	xx.x (x.x)	xx.x (x.x)
	Median	xx.x	xx.x
	Min/Max	xx/xx	xx/xx

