Week <Every 12 wks> - Combo Target	n	xx	xx
	Mean (SD)	xx.x (x.x)	xx.x (x.x)
	Median	xx.x	xx.x
	Min/Max	xx/xx	xx/xx

Notes:

(*) Change from baseline is calculated relative to Baseline 1 for values between Baseline 1 and Baseline 2; Baseline 2 for values after Baseline 2. Change from baseline values include only those patients with both a Baseline value and a value for summarized time period. n represents number of patients contributing to summary statistics.

Source: XXXX.SAS, Run on DDMMYYYY

TABLE 87. ECG Parameters - ARM C

POPULATION: SAF < Note for SAS Programmer: the following must be presented for continuous values of URBC/HPF, Bacteria, Other as well >

	Statistic	Value	Change from Baseline (*)
PR interval (ms)			
Baseline 1	n	xx	
	Mean (SD)	xx.x (x.x)	
	Median	xx.x	
	Min/Max	xx/xx	
Week 4 - Combo Target	n	xx	xx
	Mean (SD)	xx.x (x.x)	xx.x (x.x)
	Median	xx.x	xx.x
	Min/Max	xx/xx	xx/xx
Baseline 2	n	xx	
	Mean (SD)	xx.x (x.x)	
	Median	xx.x	
	Min/Max	xx/xx	
Week 4 - Nivolumab + Ipilimumab	n	xx	xx
	Mean (SD)	xx.x (x.x)	xx.x (x.x)
	Median	xx.x	xx.x
	Min/Max	xx/xx	xx/xx
Week <Every 12 wks> - Nivolumab	n	xx	xx
	Mean (SD)	xx.x (x.x)	xx.x (x.x)
	Median	xx.x	xx.x
	Min/Max	xx/xx	xx/xx
Baseline 3	n	xx	
	Mean (SD)	xx.x (x.x)	
	Median	xx.x	
	Min/Max	xx/xx	
Week 4 - Combo Target	n	xx	xx
	Mean (SD)	xx.x (x.x)	xx.x (x.x)
	Median	xx.x	xx.x
	Min/Max	xx/xx	xx/xx
Week <Every 12 wks> - Combo Target	n	xx	xx
	Mean (SD)	xx.x (x.x)	xx.x (x.x)
	Median	xx.x	xx.x
	Min/Max	xx/xx	xx/xx

Notes:

(*) Change from baseline is calculated relative to Baseline 1 for values between Baseline 1 and Baseline 2; Baseline 2 for values between Baseline 2 and Baseline 3; Baseline 3 for values after Baseline 3. Change from baseline values include only those patients with both a Baseline value and a value for summarized time period.
n represents number of patients contributing to summary statistics.

Source: XXXX.SAS, Run on DDMMYYYY

TABLE 88. Cardiological Assessments - ARM A

POPULATION: SAF

< Note for SAS Programmer: the following must be presented for each visit during the study >

	Statistic	Arm A (N=XX)
<Visit n>		
ECG Result		
Normal	n (%)	xx (xx.x%)
Abnormal	n (%)	xx (xx.x%)
Interpretation of abnormality (*)		
Not clinically significant	n (%)	xx (xx.x%)
Clinically significant	n (%)	xx (xx.x%)
Type of LVEF scan		
ECHO	n (%)	xx (xx.x%)
MUGA	n (%)	xx (xx.x%)
Interpretation of ECHO/MUGA scan		
Normal	n (%)	xx (xx.x%)
Abnormal, NCS	n (%)	xx (xx.x%)
Normal, CS	n (%)	xx (xx.x%)

Notes:

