XXX	XXX	XXXXXXXX X	XXX	XXX	XXX	DDMMYYYY	XXX	XXX	XXX	XXX	XXX	XXX	XXX	XXX	XXX	XXX	
			XXX	XXX	XXX	DDMMYYYY	XXX	XXX	XXX	XXX	XXX	XXX	XXX	XXX	XXX	XXX	
			Etc.														
XXX	XXX	XXXXXXXX X	XXX	XXX	XXX	DDMMYYYY	XXX	XXX	XXX	XXX	XXX	XXX	XXX	XXX	XXX	XXX	
			XXX	XXX	XXX	DDMMYYYY	XXX	XXX	XXX	XXX	XXX	XXX	XXX	XXX	XXX	XXX	
			Etc.														

Source: XXXX.SAS, Run on DDMMYYYY

Listing 31) ECG

POPULATION: SAF

Treatment Arm	Site	Patient Number	Visit	Was ECG performed?	If not, specify reason	Date of assessment (DDMMYYYY)	Result	If abnormal, NCS/CS	PR interval (ms)	QT interval (ms)	QRS interval (ms)	QTcB interval (ms)	Cardiac axis (°)
XXX	XXX	XXXXXXXX X	XXX	XXX	XXX	DDMMYYYY	XXX	XXX	XXX	XXX	XXX	XXX	XXX
XXX	XXX	XXXXXXXX X	XXX	XXX	XXX	DDMMYYYY	XXX	XXX	XXX	XXX	XXX	XXX	XXX
XXX	XXX	XXXXXXXX X	XXX	XXX	XXX	DDMMYYYY	XXX	XXX	XXX	XXX	XXX	XXX	XXX
XXX	XXX	XXXXXXXX X	XXX	XXX	XXX	DDMMYYYY	XXX	XXX	XXX	XXX	XXX	XXX	XXX

Source: XXXX.SAS, Run on DDMMYYYY

Listing 32) Left Ventricular Ejection Fraction

POPULATION: SAF

Treatment Arm	Site	Patient Number	Visit	Was the LVEF performed?	If not, specify reason	Date of scan (DDMMYYYY)	Type of scan	Ejection Fraction Value (%)	Scan interpretation	Specify
XXX	XXX	XXXXXXXX X	XXX	XXX	XXX	DDMMYYYY	XXX	XXX	XXX	XXX
XXX	XXX	XXXXXXXX X	XXX	XXX	XXX	DDMMYYYY	XXX	XXX	XXX	XXX
XXX	XXX	XXXXXXXX X	XXX	XXX	XXX	DDMMYYYY	XXX	XXX	XXX	XXX
XXX	XXX	XXXXXXXX X	XXX	XXX	XXX	DDMMYYYY	XXX	XXX	XXX	XXX

Source: XXXX.SAS, Run on DDMMYYYY

Listing 33) Ophthalmological examination: Visual Acuity and Intraocular pressure

POPULATION: SAF

Treatment Arm	Site	Patient Number	Visit	Performed?	Eye(s) assessed?	Visual acuity assessed?	If not, reason	Total Visual Acuity Score (ETDRS) - Left Eye (OS)	Total Visual Acuity Score (ETDRS) - Right Eye (OD)	Total Visual Acuity Snellens equivalent - Left Eye (OS)	Total Visual Acuity Snellens equivalent - Right Eye (OD)	Intraocular pressure assessed?	Intraocular pressure - left eye (OS) (mmHg)	Intraocular pressure - Right Eye (OD) (mmHg)
XXX	XXX	XXXXXXXXX X	XXX	XXX	XXX	XXX	XXX	XXX	XXX	XXX	XXX	XXX	XXX	XXX
XXX	XXX	XXXXXXXXX X	XXX	XXX	XXX	XXX	XXX	XXX	XXX	XXX	XXX	XXX	XXX	XXX
XXX	XXX	XXXXXXXXX X	XXX	XXX	XXX	XXX	XXX	XXX	XXX	XXX	XXX	XXX	XXX	XXX
XXX	XXX	XXXXXXXXX X	XXX	XXX	XXX	XXX	XXX	XXX	XXX	XXX	XXX	XXX	XXX	XXX

Source: XXXX.SAS, Run on DDMMYYYY

Listing 34) Ophthalmological examination: Indirect Dilated Fundoscopy (ophthalmoscopy)

POPULATION: SAF

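### QT change is summarised only uncorrected and with Bazett's correction, so within-arm change in QTcB partly reflects heart rate; add a Fridericia value derived per ECG from the two listed intervals

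*Supplement*

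**What the plan says.** SAP section 21.3 lists the continuous cardiological parameters: "Descriptive summaries of PR interval (ms), QT interval (ms), QRS interval (ms), QTcB interval (ms"), followed by cardiac axis and ejection fraction (in per cent). They "will be provided for actual values and changes from baseline at each visit by treatment arm". The categorical ECG outputs in that section are normal or abnormal, and the clinical significance of an abnormality.

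The shells in section 26 follow this for two arms. (Table numbers here are those printed on the shells; the list that opens section 26 numbers the ECG tables 83 to 85.) Tables 85 (Arm A) and 86 (Arm B) display the PR interval and instruct the programmer that "the following must be presented for QT, QRS, QTcB, cardiac axis, Ejection Fraction value as well". Table 87 (Arm C) also displays PR, but its note reads "the following must be presented for continuous values of URBC/HPF, Bacteria, Other as well". Those are urinalysis parameters, so the Arm C shell requests neither QT nor QTcB.

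Listing 31 holds the individual data, with columns that include "QT interval (ms") and "QTcB interval (ms") for each patient and visit. No Fridericia value, RR interval, ECG heart rate or QTc category appears in the text, abbreviations, shells or listings. Heart rate is summarised only as a vital sign, "Heart Rate (bpm"), in section 21.4.

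**The concern.** The QT interval shortens as the heart beats faster. Bazett's formula divides by the square root of RR. Where the actual dependence of QT on RR is weaker than a square root, it over-corrects as rate rises and under-corrects as rate falls. A mean change in QTcB then contains a QT component and a heart-rate component that the table cannot separate. A rise in rate adds apparent prolongation, and a fall can mask a real one. Uncorrected QT does not settle the matter, because it moves with rate in the other direction.

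At stake is how the ECG change tables within each arm are read. The remedy needs no new measurement, because QT and QTcB from the same tracing together determine RR.

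**Working it through.** The SAP states no QT figure to reproduce. The check has three parts.

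**1. Can QTcF be recovered from what is listed?** Inputs: QT and QTcB per ECG (Listing 31), with RR in seconds.

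- Bazett: QTcB = QT / RR^(1/2), so RR = (QT / QTcB)².
- Fridericia: QTcF = QT / RR^(1/3) = QT × (QTcB / QT)^(2/3) = (QT × QTcB²)^(1/3).

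Over QT 280 to 520 ms and heart rate 40 to 140 bpm, the identity held to below 10⁻¹² ms. With QTcB rounded to the nearest millisecond, the largest error was 0.35 ms. Rounding QT as well adds at most about (1/3) × (QTcF/QT) × 0.5 ms. At 140 bpm QTcF/QT = (140/60)^(1/3) = 1.33, so this is about 0.2 ms and the total stays under 1 ms.

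**2. How far does QTcB move when only rate changes?** Assumptions, none of them from the documents: QT = c × RR^(1/3), c = 410 ms, RR = 60/HR. Then QTcB = c × RR^(1/3 − 1/2) = c × (HR/60)^(1/6).

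| Heart rate (bpm) | Change in QT (ms) | QTcB (ms) | Change in QTcB (ms) | Change in QTcF (ms) |
|---|---|---|---|---|
| 60 to 65 | −10.8 | 410.0 to 415.5 | +5.5 | 0 |
| 70 to 75 | −8.9 | 420.7 to 425.5 | +4.9 | 0 |
| 60 to 70 | −20.5 | 410.0 to 420.7 | +10.7 | 0 |
| 60 to 75 | −29.4 | 410.0 to 425.5 | +15.5 | 0 |

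With c = 400 ms, 60 to 70 bpm gives QT −20.0 and QTcB +10.4 ms, and a fall from 80 to 60 bpm gives QTcB −19.6 ms. Larger rises give more: at c = 410 ms, QTcB is 438.7 ms at 90 bpm and 446.4 ms at 100 bpm, that is +28.7 and +36.4 ms from 60 bpm.

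The zeros in the last column follow from the assumed exponent. In general, if QT = c × RR^b, then QTcB varies as RR^(b − 1/2) and QTcF as RR^(b − 1/3). The direction of the QTcB artefact holds for any b below 1/2. QTcF is free of rate only at b = 1/3, and it is the less rate-dependent of the two for any b below 5/12, the midpoint of 1/3 and 1/2.

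**3. Do the other planned tables separate the two components?** Heart rate is summarised separately and is not paired with the ECG. In the nivolumab plus ipilimumab block of Arm A, the ECG shell (Table 85) has a Week 4 visit, whereas the vital-signs shell (Table 91) has visits every 3 weeks, four times. A reader cannot match rate to QT there, and no visit-level summary of vital signs gives a correction per tracing.

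**The case against.** The strongest reply is that nothing in the plan turns on QTcB. Section 8.3 excludes comparative tests between arms, Tables 85 to 87 are separate shells by arm, and section 21.3 sets no QTc threshold or outlier category. A reader might infer that the choice of Bazett would classify patients as prolonged or distort a comparison of the sequences. The documents do not support that: no such classification or comparison is planned. This part stands and limits the point to descriptive within-arm change.

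It is also fair that the illustration uses Fridericia's own model and assumed rate shifts, and that a mean change as large as those shown would need the group's mean rate to move by that amount. The size is therefore conditional. The direction is less so, since it needs only an exponent below one half.

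Heart rate is reported in section 21.4, and QT and QTcB moving in opposite directions would be a warning sign. That helps an alert reader, but it does not quantify the rate component, for the reasons in part 3 of the working.

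Two further limits stand. The SAP does not say how QTcB is obtained, and section 9.3 rules out imputation, so the derivation applies only where both values are present and come from the same tracing. Section 4.6 says the analysis is unchanged from the protocol, which is not shown, and the SAP ranks no ECG parameter. There is thus no basis here for displacing QTcB or naming QTcF the main measure. The new baseline for each treatment block (section 8.4) is a separate matter that would affect QTcF equally.

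**Conclusion.** The point holds as a small improvement to descriptive safety output. Section 21.3, Tables 85 and 86 and Listing 31 carry only uncorrected QT and QTcB, so within-arm change from baseline in QTcB partly reflects change in heart rate. Under the stated assumptions (cube-root relation, corrected QT of about 400 to 410 ms) the artefact is about +5 ms for a 5 bpm rise, about +10 ms for 60 to 70 bpm and about +16 ms for 60 to 75 bpm. How much of this would arise in the trial cannot be judged from the documents, which contain no heart-rate data. Nothing is lost irrecoverably, since both intervals are listed by patient. The Table 87 note is a plain drafting error: as written, the Arm C shell does not deliver what section 21.3 promises.

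**What to change.** In section 21.3, Tables 85 to 87 and Listing 31, add QTcF = (QT × QTcB²)^(1/3). Derive it for each ECG before summarising, never from visit means, and only where QT and QTcB are both present from the same tracing. Report it alongside QTcB, which stays. State in section 21.3 that QTcB is taken to be the Bazett value from that tracing.

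In the same edit, replace the Table 87 programmer note with the parameter list used for Tables 85 and 86, plus QTcF.

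The cost is one derived variable, one listing column and one extra block of rows per ECG table, with rounding error under about 1 ms. No new data collection is needed.
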